**1. Introduction and Purpose**

1.1 The purpose of this study is to compare the functional outcomes of patients with shoulder pathology treated with either ketorolac or corticosteroid injections, in a randomized double-blinded study. We will compare the effectiveness of ketorolac compared to corticosteroid.

1.2 Specific Aim 1:

Hypothesis 1: Injection of the shoulder (in the subacromial space) with Ketorolac will be more effective than corticosteroid injection for the treatment of a variety of shoulder pathologies.

1.3 The risks associated with this study primarily concern adverse reactions to the study drugs. The drugs used in this study are not narcotics or habit-forming but can have side effects. The patient's physician will screen for any heart, intestinal, or kidney disease or condition that would increase the chance for the patient to have an unwanted side effect.

**2. Background** Nonoperative management is the first line of treatment for a variety of painful shoulder pathologies including atraumatic full thickness rotator cuff tears, rotator cuff tendinitis, and rotator cuff tear arthropathy. Conservative management consists of rest/activity modification, ice, physical therapy, nonsteroidal anti-inflammatory (NSAIDs) medications and injections. Frequently, the pain associated with shoulder pathology is secondary to either synovial or bursal inflammation. The goal of injections is to reduce inflammation, decreasing pain and allowing the patient to better tolerate physical therapy in attempts to restore proper shoulder kinematics.

Corticosteroid injections are a commonly used treatment modality in patients who have failed to respond to other less invasive conservative management options such as systemic NSAID medications and physical therapy. Several studies have demonstrated significant improvements with regards to pain relief and range of motion with the use of corticosteroid injections in the subacromial space for the treatment of rotator cuff tendinitis/ full thickness rotator cuff tears,[1-9].

The frequency of corticosteroid injections is limited by associated side effects on connective tissue with numerous reports in the literature of spontaneous tendon rupture following local injections. Additionally, there have been several animal studies that demonstrate corticosteroid exposure can result in tendon and ligament atrophy, fragmentation of collagen bundles, delayed healing, articular cartilage changes, and decreased mechanical properties.[10-14] Furthermore, a study by Wei et al.[14] demonstrated that a single

dose of methylprednisolone to healthy uninjured rotator cuff tendons can have an appreciable effect on biomechanical properties and collagen expression.

Given that it is hypothesized the efficacy of corticosteroid injection is the anti-inflammatory effect, one could extrapolate that injection of NSAID medication may provide similar benefit. Recently Min et al.[5] performed a prospective randomized trial comparing corticosteroid with ketorolac subacromial injection for the treatment of patients with rotator cuff tendinitis. The authors found that ketorolac provided significantly greater improvements in UCLA shoulder rating at 4 weeks as compared to triamcinolone and both medications provided equivalent improvements in VAS pain relief. Ketorolac is a strong nonsteroidal anti-inflammatory agent that can be delivered in an injectable for making it ideal for use in treatment of patients with shoulder pathology. There have been a few studies [15-17] examining the efficacy and safety of NSAIDS intraarticular injections, but no specific studies examining the effects of these medications on rotator cuff tendon. Dogan et al.[15] examined the effects of ketorolac and morphine intraarticular injection in rabbit knees and found synovial membrane inflammatory cell infiltration with minimal histopathologic changes to the synovium. The authors concluded that ketorolac can be used as an intraarticular injection safely. To our knowledge there are no studies examining the effect of ketorolac on rotator cuff tendon.

**Adverse Events:** Three prior randomized controlled trials have been published using ketorolac in one arm of the trial. In these three studies, no clinically significant adverse event was detected for those getting ketorolac as a post-op intra-articular regional analgesic (Axelsson K et al, Anesth Analg, 2008 and Cho NS et al, Am J Sports Med, 2007) or as an injection therapy (Min KS, J Should Elbow Surg, 2013). While we acknowledge that Ketorolac injections represents “off-label” use The Min article sets specific precedent in the medical literature to support the safe use of this modality. This published study was a double-blind randomized controlled using ketorolac and kenalog with similar dosage and found ketorolac to be equivalent if not superior in efficacy in regards to self-report of function, range of motion, and patient satisfaction. Most importantly, no adverse events were reported for the ketorolac arm of the trial (n = 17). 1 subject who received the kenalog injected experienced a fainting episode secondary to a vasovagal reaction with no long term consequence. We believe these papers provide support for the safety and potential value of a FDA approved intra-articular medication injection and our study aim is to validate the findings of this report in a wider variety of patients with soft-tissue pathologies of the shoulder.

### **3. Concise Summary of Project**

**3.1 Study Design:** The proposed study is a three arm, double-blinded, prospective randomized controlled clinical trial with follow-up immediately after the injection and at day 2, and weeks 1, 2, 4, 6, and 12. In this study we will compare the effectiveness of ketorolac compared to corticosteroid.

Ketorolac is an injectable solution which should be stored at 15 C to 30 C (59 F to 86 F) and protected from light. Marcaine (Bupivacaine) should be stored at room temperature, between 20 C to 25 C (68 F to 77 F). And Kenalog (triamcinolone) should be stored at controlled room temperature, 20°–25°C (68°–77°F), avoid freezing and protect from light. Do not refrigerate.[18]

Medications are stored in a locked cabinet at room temperature. The Research Team will prepare the appropriate injection medication according to group assignment at the time of the appointment. Injections will not be prepared beforehand. Injections will be prepared by inserting the syringe into both bottles and drawing the required amount. The syringe contents will be masked from the physician.

**Study Groups:** Subjects being seen for a rotator cuff injury will be randomized into one of three treatment groups pertaining to their pathology. The intervention will begin once the subject has consented and answered the Baseline Outcome Shoulder Questionnaire. The Baseline Outcome Questionnaire consists of the Visual Analog Score, American Shoulder and Elbow Score, Single Assessment Numeric Evaluation, Pittsburgh Sleep Quality Index, SF-12, range of motion and measure the subjects shoulder strength by using a

dynamometer, and questions pertaining to patient characteristics, injury characteristics, co-morbidities, patient history, medications, and demographics.

A dynamometer is a small, hand-held device which the subject presses against. By pressing against the device, it measures the strength of their shoulder.

#### Full Thickness Rotator Cuff Tear:

Group 1 (control): will receive an injection of 5 cc 0.25% Marcaine without epinephrine

Group 2 (ketorolac): will receive an injection of 3 cc 0.25% Marcaine without epinephrine and 2 cc ketorolac 30 mg/ml

Group 3 (kenalog): 4 cc 0.25% Marcaine without epinephrine and 1 cc triamcinolone.

#### Rotator Cuff Tendinitis

Group 1 (control): will receive an injection of 5 cc 0.25% Marcaine without epinephrine

Group 2 (ketorolac): will receive an injection of 3 cc 0.25% Marcaine without epinephrine and 2cc ketorolac 30 mg/ml

Group 3 (kenalog): 4 cc 0.25% Marcaine without epinephrine and 1 cc triamcinolone.

### 3.3 "DRUG CLASS AND MECHANISM:

Ketorolac is a member of a class of drugs called nonsteroidal antinflammatory drugs (NSAIDs) that are used for treating inflammation and pain. Other drugs in this class include ibuprofen (Motrin) and naproxen (Naprosyn, Aleve), but ketorolac is more effective than other NSAIDs in reducing pain from both inflammatory and non-inflammatory causes. Ketorolac reduces the production of prostaglandins, chemicals that cells of the immune system make that cause the redness, fever, and pain of inflammation and that also are believed to be important in the production of non-inflammatory pain. It does this by blocking the enzymes that cells use to make prostaglandins (cyclooxygenase 1 and 2). As a result, pain as well as inflammation and its signs and symptoms - redness, swelling, fever, and pain - are reduced. The FDA approved ketorolac in November 1989." [19]

"Marcaine (Bupivacaine) is a local anesthetic that is similar to lidocaine and mepivacaine (amide type). Bupivacaine, like other local anesthetics reduces the flow of sodium in and out of nerves. This decreases the initiation and transfer of nerve signals in the area in which the drug is applied. This blockage leads first to a loss of sensation of pain, then temperature, touch, deep pressure, and muscle control. The concentration of the drug will determine how quickly it starts working. The FDA approved bupivacaine in October 1972." [20]

Kenalog is a corticosteroid; synthetic glucocorticoid analogs with anti-inflammatory effects. [21]

### 3.4 Independent Variable: One of three injection protocols.

#### Dependent Variables

- Primary Outcome Variable:
  - Visual Analog Scale
  - American Shoulder and Elbow Score
- Secondary Outcome Variable:
  - Single Assessment Numeric Evaluation (SANE)
  - Pittsburgh Sleep Quality Index
  - SF-12

**Functional Outcome:** Visual Analog Scale (VAS) is utilized to measure level or intensity of pain. The scale consists of a horizontal (HVAS) or vertical (VHAS) line, usually 10 cm in length [22] with a descriptor at both ends; the left side reading “no pain at all” and the right side reading “worst pain imaginable.” While this scale is very subjective, patients have an easier time reporting pain on a continuum rather than jumping from categories of none, mild, moderate [23] or severe.

**American Shoulder and Elbow Score (ASES):** is a standardized, 17 item [24], patient self-report tool, which can be completed in about 3 minutes. The patient self-reported section consists of three sections: pain, instability, and activities of daily living. The tool also consists of a physician assessment which includes range of motion, signs, strength, and instability.[25]

**Single Assessment Numeric Evaluation (SANE):** “is an outcome measurement tool used to record the patient’s self-reported function [26]. It is implemented on a scale of 0-100 and correlated with a scale of function from 0-100%. The 100% representing full function (or function prior to injury) and 0% representing no function.”

**Pittsburgh Sleep Quality Index (PSQI):** is a standardized measure for quality of sleep. The tool consists of 24 questions which differentiate “good” and “poor” sleepers and is easy to use for both the patient and the researchers.[27]

**SF-12:** is a standardized general health survey which measures physical and mental health.

## 4. Study Procedures

4.1 Subjects will be identified in clinic following evaluation by the clinician and determination/ diagnosis of the etiology of shoulder pain. During the initial visit, the physician will conduct the standard clinic visit. Female subjects of child-bearing age will not be enrolled into the study. Documentation of female subjects having been permanently sterilized or postmenopausal will be recorded in their medical record.

During the initial visit, the research team will abstract the following information from the subject's medical record

- Demographics
- Medications
- Patient Characteristics
- Injury Characteristics
- Co-morbidities
- Patient History

Subjects identified as meeting inclusion criteria for the study will be asked if they are willing to participate in the study and if agreeable will undergo the informed consent process.

#### *Enrollment*

Once a patient is identified as meeting inclusion criteria they will be informed of the study and asked if they are willing to participate. They will be informed that enrollment is completely voluntary and will not impact treatment of the underlying shoulder pathology. Additionally, potential subjects will be informed that both corticosteroid and ketorolac are safe and effective modalities for injection that would be used as part of routine treatment of shoulder pain. These medications are commonly mixed with an anesthetic such as Marcaine for both diagnostic and therapeutic means.

The anesthetic allows both patient and clinician almost immediate feedback with resolution of pain once the anesthetic takes effect-providing information that the injection was properly delivered into the subacromial space.

The subjects will be informed that they will be randomized into one of 3 treatment groups and will be asked to complete a questionnaire about the status of the shoulder as well as follow-up questions at predetermined intervals for a total of 12 weeks. They will also be informed that all other treatment of the shoulder will proceed as is standard based on the pathology (i.e. physical therapy, oral medications) and eligibility for surgical intervention should these conservative measures fail to provide relief of symptoms. If a patient agrees to participate in the study they will undergo the informed consent process by the research staff. Research staff will determine if the patient continues to be eligible according to inclusion/exclusion criteria and if the patient is willing to participate in the follow-up.

Once consented into this study, baseline data regarding patient characteristics, injury characteristics, and medical history and co-morbidities, including current use of pain medication, will be collected and entered into the data collection system. Some of this information will be obtained via the Outcome Shoulder Questionnaire with the patient.

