#### *Randomization*

Subjects will be randomized to one of three injection groups: Group 1 will receive the control injection (Marcaine), Group 2 will receive a NSAID injection (Ketorolac & Marcaine), and Group 3 will receive a steroid injection (Kenalog & Marcaine).

Five to 10 minutes following injection, subjects will be asked how the injection changed shoulder symptoms by utilizing the Visual Analog Scale (VAS) and Single Assessment Numeric Evaluation (SANE).

Patients will be contacted by phone to complete a follow-up questionnaire 2 days after the injection as well as at 1, 2, and 4 weeks. The subjects will be followed up in clinic at 6 and 12 weeks, after the shoulder injection, which is standard clinical practice with completion of the outcomes questionnaire. Subjects will reach study completion at 12 weeks following injection.

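### The Enrollment text has staff tell potential subjects, before consent, that both drugs are safe, effective and routine and that joining does not affect treatment; other sections of the protocol contradict this

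*Combined protocol and SAP*

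**What the plan says.** Section 4, Enrollment, sets out what staff tell a patient who appears eligible. On the drugs: "potential subjects will be informed that both corticosteroid and ketorolac are safe and effective modalities for injection". The same sentence goes on to describe them as injections "that would be used as part of routine treatment of shoulder pain". On the effect of joining: "enrollment is completely voluntary and will not impact treatment of the underlying shoulder pathology". The same text says that subjects hear that there are three randomised groups and that other shoulder care continues as standard. It mentions Marcaine as an anaesthetic with which the two drugs are commonly mixed. It does not say that one group receives Marcaine alone. Those who agree then go through the consent process.

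Other sections read differently:

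- Section 2, Adverse Events, acknowledges that "Ketorolac injections represents “off-label” use". The one trial of ketorolac as an injection therapy cited there is summarised as "no adverse events were reported for the ketorolac arm of the trial (n = 17"). The other two cited trials used it for post-operative analgesia. The stated aim is to validate the injection trial in a wider range of patients.
- Section 2, Background: "To our knowledge there are no studies examining the effect of ketorolac on rotator cuff tendon". The same section cites numerous reports of spontaneous tendon rupture after local corticosteroid injection.
- The text that follows 4.6 presents a safe and effective alternative as something that the results of this study would make available.
- Section 4, Randomization: "Group 1 will receive the control injection (Marcaine"), with no second drug. Section 14 allocates 1:1:1. Section 4.6 says that randomising the injection is the only change to clinic practice.

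**The concern.** The Enrollment text presents as settled two things that the protocol elsewhere treats as open or as untrue.

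The first is the safety and effectiveness of the drugs. The trial is run to compare ketorolac with corticosteroid, with an anaesthetic-only control, and the protocol acknowledges both the off-label status and the evidence gap. The script mentions neither.

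The second is the effect of joining. The injection is the treatment under study. Once a patient joins, it is chosen by randomisation and in one arm contains neither drug.

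At stake is the accuracy of what patients are told when they decide whether to receive an off-label injection. These statements come before the consent process, so an accurate consent form would have to correct what the patient has just heard. No estimand, sample size or analysis is affected.

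**Working it through.** **1. Share of subjects given anaesthetic only.** Inputs from 14.2: 66 subjects per arm, 3 arms, 2 diagnostic categories, stated total 400.

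- Plan's total: 66 × 3 × 2 = 396, which reproduces the rounded 400.
- Marcaine-only arm: 66 × 2 = 132.
- Share: 132/396 = 33.3%, or 132/400 = 33.0%. Taking the rounded total directly, 400/3 = 133.

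So about one subject in three receives neither ketorolac nor corticosteroid.

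**2. What 0 events in 17 can support.** Input from section 2, Adverse Events: no adverse events among 17 ketorolac subjects. With zero events in n subjects, the exact upper limit for the event rate is 1 − α^(1/n).

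- One-sided 95%: 1 − 0.05^(1/17) = 0.162, or 16.2%.
- Upper end of the two-sided 95% interval: 1 − 0.025^(1/17) = 0.195, or 19.5%.

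This limit is for any adverse event in that one arm.

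**3. The statements side by side.**

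| Enrollment text | Elsewhere in the protocol |
|---|---|
| Ketorolac is safe and effective | Off-label; one injection-therapy trial with 17 ketorolac subjects; no known tendon study (section 2). A safe and effective option is an expected product of this study (text after 4.6) |
| Corticosteroid is safe and effective | Benefit on pain and motion is cited, but so are reports of tendon rupture after injection (section 2) |
| Joining does not affect treatment of the shoulder condition | The injection is randomised, and this is a change in practice (4.6); one arm of three is Marcaine alone (sections 3.1, 4 and 14) |

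The right-hand entries cannot all stand with the unqualified statements on the left. Where the Background supports part of a statement, as with the benefit of corticosteroid, the script still omits the qualification that goes with it.

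**The case against.** The strongest reply is that the consent form is not in the review copy. Section 9.2 provides a joint conversation with the physician and a pamphlet on risks and benefits, and the off-label status and the control arm may well be disclosed there. This stands as a limit: a reader might infer that subjects are never told these things, and the documents do not show that. It does not repair the Enrollment text, which prescribes its own statements.

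The assurance about treatment sits in the voluntariness sentence. It may mean only that care does not depend on joining, since the same text discloses randomisation and says that other care is standard. That reading is reasonable, but the sentence does not contain the limit. Section 9.4 and the Undue Influence paragraph give similar assurances in narrower terms, so the narrower wording is available.

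Off-label use does not by itself contradict routine, safe or effective use. Nor is there an absence of clinical data: section 2 cites a randomised trial of subacromial ketorolac in rotator cuff tendinitis that favoured ketorolac on a shoulder rating at 4 weeks. The gap that the authors acknowledge concerns the effect on tendon. Both points stand; the defect is that the script leaves out the qualifications.

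Three further inferences are tempting and are not supported:

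- **The 16.2% as a limit on serious harm.** It covers any event; the same trial counted a vasovagal faint in the other arm. The two post-operative trials, reported without clinically significant events, are not in the calculation because the protocol does not give their sizes.
- **Expectation bias in the self-reported outcomes.** Both active drugs are described alike, so the ketorolac–corticosteroid comparison gains no differential expectation from the script. Against control, subjects would have to guess their arm despite masked syringes, equal 5 cc volumes and blinded billing.
- **Subjects discounting early symptoms.** Section 10.1 lists symptoms for which to seek help, 10.3 promises active monitoring, and section 11 has adverse events assessed at calls and visits.

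**Conclusion.** The concern holds as an internal contradiction in what the protocol tells staff to say before consent. The unqualified statement on safety, effectiveness and routine use conflicts with section 2 and with the text after 4.6. The assurance about treatment, as worded, conflicts with 4.6 and with an allocation that gives about one subject in three (132 of 396) Marcaine alone. The one injection-therapy arm cited for safety leaves an adverse event rate of up to 16.2% open.

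This rests on the Enrollment wording being used as written, and on 1:1:1 allocation at the planned numbers. It makes no finding about the content of the consent form or pamphlet, about bias in the outcomes, or about the rate of serious harm. It should be corrected because it concerns the accuracy of risk information and the correction is cheap.

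**What to change.** Amend two sentences in section 4, Enrollment.

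- Keep the statement that enrolment is voluntary. Limit the assurance that follows it, for example: *the decision whether to join will not affect the care you are otherwise offered.*
- Replace the sentence on safe, effective and routine injections with, for example: *ketorolac injection here is an off-label use; its safety and its effect compared with corticosteroid and with anaesthetic alone are being studied; one of the three groups receives local anaesthetic without either drug.*

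Then check that the pamphlet in 9.2 and the consent form say the same. Section 4.6 already says that the injection is randomised and needs no change. No arm, dose, outcome or analysis is altered.

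Cost: a wording amendment with IRB review, and possibly slightly slower accrual.

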#### *Injection Procedure Description:*

The posterior aspect of the shoulder will be prepped in a sterile fashion with chlorhexidine scrub. The anatomic shoulder landmarks will be palpated under sterile conditions and using a standard posterior shoulder portal a subacromial injection will be given. For those subjects in which subacromial injection would be appropriate (i.e. rotator cuff disease) a 20 gauge needle is inserted posteriorly along the posterior border of the acromion, once contact is made with the underlying bone the needle is slid beneath the acromion and directed to the anterolateral aspect of the subacromial space then injection medication delivered. Dosages for each of the three group assignments will be as follows: Group 1 (control): 5 cc 0.25% Marcaine without epinephrine; Group 2 (ketorolac): 3 cc 0.25% Marcaine without epinephrine and 2 cc Ketorolac 30 mg/ml; Group 3 (kenalog): 4 cc 0.25% Marcaine without epinephrine and 1 cc kenalog.

The Research Team will prepare the appropriate injection medication according to group assignment and the syringe contents will be masked from the physician. Each injection will contain a total of 5 cc.

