## **9. RECRUITMENT METHODS and CONSENTING PROCESS:**

### *9.1 Screening*

The treating physicians will identify potentially eligible subjects from the UT Southwestern Ambulatory Outpatient Orthopaedic Surgery clinic and John Hopkins clinics: Johns Hopkins Orthopaedics, Johns Hopkins Community Physicians, and Southern Maryland Orthopaedic and Sports Medicine Division of Centers for Advanced Orthopaedics. Study Investigators and their research teams will assess subjects for the study and include a review of the medical record to ensure none of the study exclusion criteria are met. The study will be discussed with potentially eligible subjects.

*9.2 Recruitment:* Only those presenting for a shoulder evaluation at the UT Southwestern Ambulatory Outpatient Orthopaedic Surgery clinic and John Hopkins clinics: Johns Hopkins Orthopaedics, Johns Hopkins Community Physicians, and Southern Maryland Orthopaedic and Sports Medicine Division of Centers for Advanced Orthopaedics, who meet inclusion criteria will be recruited for potential participation in the study.

Informed consent will be obtained prior to initiation of the study. The physician will be involved in the consent conversation. The conversation will be initiated by the research team and physician together. The consent process will involve a dialogue. Specifically, patients and their families will be provided with a pamphlet describing the study, the risks and benefits of participation and what will be expected of them if they choose to participate.

Consent must be obtained from the patient in this study; no legally authorized representatives or surrogates may consent on behalf of the patient. This is due to the subjective nature of assessing pain. All recruitment materials will be provided in English.

9.3 Screening, enrollment, and informed consent process will take place in a private treatment area.

9.4 If a patient decides to withdraw from the study, he/she may do so at any point by informing the Principal Investigator in writing. A 'Note to File' must be inserted into the patient's chart and research file stating the patient formally withdrew from the study with the reason (if given). The patient will be assured that the medical care which they receive will not be affected should they elect to discontinue participation in the study.

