Randomization: Subjects will be recruited from the UT Southwestern Orthopaedic Surgery Clinic and John Hopkins clinics: Johns Hopkins Orthopaedics, Johns Hopkins Community Physicians, and Southern Maryland Orthopaedic and Sports Medicine Division of Centers for Advanced Orthopaedics, from patients who meet the inclusion criteria. As this study design will be prospective randomized double-blinded, we will utilize computer generated block randomization technique. After identifying a patient who meets the inclusion criteria by history, physical examination, and obtaining informed consent, HIPPA, health screen, and baseline measurements, subjects will be randomized into one of three cohorts: 1) Control (Marcaine injection), 2) NSAID injection (ketorolac & Marcaine injection), or 3) Steroid injection (kenalog & Marcaine injection). To ensure that the number of subjects is about the same in the three arms of the study, the randomization scheme will assign patients in a 1:1:1 ratio in randomly permuted blocks of assignments stratified by clinical center. Block size will be determined randomly and the patient will be the unit of randomization.

Enrollment and randomization results will be documented in the patient's chart according to protocol. The randomization allocation will be blinded to both the patient (initially) as well as the physician performing the injection and the investigator conducting statistical analysis of the results. Given the nature of this study looking at the effects of this intervention on multiple shoulder pathologies we anticipate approximately 200 subjects per diagnostic category would be needed for enrollment and complete follow-up.

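### The unmasked research team both prepares syringes by arm and makes the last eligibility check, so with centre-stratified permuted blocks those admitting subjects may guess the next arm better than chance

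*Combined protocol and SAP*

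**What the plan says.** **Who admits subjects.** Section 9.1 starts with the clinician: "The treating physicians will identify potentially eligible subjects". It then brings in the study team: "Study Investigators and their research teams will assess subjects for the study". Section 9.2 has the physician and the research team open the consent discussion jointly. The Enrollment text in section 4 places a last check with staff: "Research staff will determine if the patient continues to be eligible according to inclusion/exclusion criteria".

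**Who knows the arm.** Section 3.1 states: "The Research Team will prepare the appropriate injection medication according to group assignment at the time of the appointment". The injection procedure in section 4 repeats this and names the person who is masked: "The Research Team will prepare the appropriate injection medication according to group assignment and the syringe contents will be masked from the physician".

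**Who is blinded.** The Randomization text in section 14 says: "The randomization allocation will be blinded to both the patient (initially) as well as the physician performing the injection". It adds the investigator who analyses the results. Section 14.1 also lists the study investigator and the examiner who injects. The research team is in neither list, and could not be while it fills syringes by arm. Section 14 further provides: "Enrollment and randomization results will be documented in the patient's chart according to protocol".

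**How subjects are allocated.** Assignments come from a computer-generated 1:1:1 scheme, "in randomly permuted blocks of assignments stratified by clinical center". Block size is itself chosen at random, and no sizes are given. Randomization follows inclusion, consent and baseline measurement. No central service, sealed envelopes or independent holder of the list is described.

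**The concern.** Blinding the injector and the patient protects what happens after assignment. Concealment protects the step before it: the person deciding whether a patient enters should have no better idea than chance of which arm comes next. Here the team that makes the last eligibility decision also learns each assignment as it is made, and permuted blocks make past assignments informative about the next.

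There is room for such a guess to act. Section 7 excludes a recent prior injection without defining recent. It also excludes patients thought likely to have serious difficulty with follow-up or who live too far away, and the Enrollment text adds willingness to be followed. One arm is anaesthetic alone, and sections 1.2 and 4 state favourable expectations of ketorolac. A staff member could, even without intending to, admit or defer a borderline patient according to the arm expected. The arms would then differ at baseline for reasons other than chance. Adjustment can address imbalance in what was measured, such as baseline VAS and ASES, but not selection on unmeasured features.

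**Working it through.** The plan gives no figure on predictability, so there is none to reproduce. The check has two parts.

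**1. Roles side by side**

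| Step | Who | Knows assignments? |
|---|---|---|
| Diagnosis, first identification (4.1, 9.1) | Treating physician | Masked if also the injector |
| Eligibility review (9.1) | Investigators and research teams | Investigators blinded; team not listed |
| Consent discussion (9.2) | Physician and research team together | Mixed |
| Last eligibility check (Enrollment) | Research staff | Not listed as blinded |
| Syringe preparation (3.1, injection procedure) | Research team | Yes, necessarily |

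No text says that the people in the last two rows must be different. Equally, none says that they are the same individual.

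**2. How informative past assignments are**

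Inputs from section 14: ratio 1:1:1, permuted blocks, random block size, stratification by centre only, hence one running sequence per centre. Assumed: the block sizes, taken as multiples of 3 from 3 to 12.

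- No knowledge of earlier assignments: 1/3 = 33.3% correct.
- Exact benchmark, fixed blocks of 3: the three positions are guessed with probability 1/3, 1/2 and 1, so (1/3 + 1/2 + 1)/3 = 11/18 = 61.1%. Simulation gives 61%. The plan does not use fixed blocks; this only validates the simulation.
- Random block sizes, all earlier assignments at the centre known, simulated with 100 and 200 subjects per centre:

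| Assumed sizes | Best guess correct | Assignments certain |
|---|---|---|
| 3, 6 | about 58% | about 9% |
| 3, 6, 9 | about 55% | about 4% |
| 6, 9, 12 | 52% to 53% | about 2% |

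The best guess assumes that the guesser knows the set of possible sizes. That knowledge is hardly needed: naming the arm used least so far, with ties broken at random, gives 57% to 58%, 55% and 53% for the same three sets. For comparison, 33% of assignments are certain with fixed blocks of 3 and 19% to 20% with fixed blocks of 6. Random sizes therefore remove most of the certainty but leave a gain over chance of 52 − 33 = 19 to 58 − 33 = 25 percentage points.

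- Partial knowledge: if a person sees a random half of earlier assignments and names the arm seen least, the guess is right about 38% of the time in a centre of 60 subjects, a gain of 38 − 33 = 5 points. In a check of the same rule with longer sequences, this fell to about 37% at 100 subjects and 36% at 200.

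The advantage thus depends mostly on how much of the sequence the admitting person has seen, which is what separating the roles would limit.

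**The case against.** The strongest reply has five parts.

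- **Order is already fixed.** Section 14 randomizes only after inclusion, consent and baseline, and section 3.1 says that injections are not made up in advance. This stands: a reader might infer that the plan leaves assignment open until after eligibility is argued, and the documents do not support that. But order does not prevent a guess made before randomization.
- **Block sizes are random.** This also stands as a safeguard. A reader might infer that staff can predict the next assignment. With about 2% to 9% of assignments certain, the supportable statement is that they can guess better than chance.
- **The team does not control entry.** Treating physicians identify candidates, investigators share in eligibility review, and the physician joins the consent discussion. This stands and narrows the opening, though the last check still lies with research staff.
- **A team is not one person.** A reader might infer that whoever admits subjects knows every earlier assignment. The documents name a research team and research staff, not an individual, and do not say who prepares each syringe at a clinic. The 52% to 58% is therefore the full-knowledge case and 38% an illustration of partial knowledge.
- **No effect on the result is shown.** Correct. A guessing rate is not a bias; someone must also act on the guess. The documents give no basis for estimating a shift in the treatment effect.

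What survives is that the plan leaves eligibility confirmation and knowledge of assignments in the same hands, and describes no mechanism that hides the sequence from enrolling staff.

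**Conclusion.** The point holds as a gap in allocation concealment that should be closed, at little cost. Staff who have seen the earlier assignments at a centre could guess the next arm about 52% to 58% of the time instead of 33%, falling to about 38% if they have seen half. These rates rest on assumed random block sizes between 3 and 12 and, for the higher range, on full knowledge of the sequence at that centre. Together with the discretionary exclusions in section 7, this makes selection at entry possible. The documents do not show that it has happened or will happen, nor how large any resulting bias would be.

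**What to change.** **Section 3.1 and Enrollment.** State that staff who prepare injections, or who have access to earlier assignments at a clinic, do not consent subjects or confirm eligibility there. Divide these duties among existing staff.

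**Section 14, Randomization.** Keep block sizes and the running sequence from enrolling staff, including by limiting who can read the assignment recorded in the chart. Require eligibility and diagnosis to be recorded before the assignment is released; this makes explicit the order that section 14 already sets.

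**Reconcile the sequence.** The text on the baseline questionnaire in section 4 randomizes before that questionnaire, whereas section 14 randomizes after baseline measurements. The two should agree.

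The arms, endpoints, sample size and blocking stay as they are. The cost is a recording step, a written split of duties, and less scheduling flexibility at small clinics where few staff are available.
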